### **12.2 Statistical Analysis**

#### **Analysis principles**

- Primary analysis will be conducted on an intention-to-treat basis (patients with protocol violations are analyzed per the assigned treatment arm).
- All hypothesis tests will be two sided, with an  $\alpha$  of 0.05 unless otherwise specified.
- All analyses will be unadjusted unless otherwise specified.
- Subgroup analyses will be performed irrespective of treatment efficacy.

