- Composite of any of: presence of lip ulcer, endotracheal tube dislodgement, or facial skin tears from the time of randomization to the earlier of death or 48 hours after extubation

Secondary Endpoints:

- Presence of Lip Ulcer
- Endotracheal tube dislodgement
- Ventilator associated pneumonia incidence

- Facial skin tears
- Ventilator-free days

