## **8.0 Data Collection**

All data will be collected non-invasively and will already be a part of clinical data obtained in usual ICU care at the bedside or in the medical record. No additional data will be obtained beyond that which is obtained by bedside observation and from the electronic medical record.

**Baseline:** Age, gender, height, weight, race, active medical problems at the time of intubation, active comorbidities complicating intubation, indication for intubation, whether it is a reintubation, whether the face was soiled during the intubation

**Periprocedural:** Depth of tube as measured at lip line and position in mouth (ie 22 cm at the lip, midline) at time of securement

**In-Hospital Outcomes:** days on mechanical ventilator, ICU mortality, mortality for ventilator free days, oral mucosa assessment, facial skin integrity assessment, frequency of endotracheal tube repositioning, endotracheal tube dislodgements – defined as either complete

Principal Investigator: [name], ACNP-BC

Study Title: Adhesive Versus Endotracheal Tube Fastener

Institution: Vanderbilt University Medical Center

Version Date: 3/21/2018

dislodgement of the endotracheal tube (i.e. accidental extubation) or needing to reposition the endotracheal tube more than 1 cm (i.e. need to pull ETT back 2+ cm or move it down 2+ cm).

The following study endpoints will be collected if they occur anytime between randomization and the earlier of death, hospital discharge, tracheostomy placement, or 48 hours after extubation: lip ulcers, facial skin tears, tube dislodgement, and ventilator associated pneumonia.

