## **12.0 Statistical Considerations**

### **12.1 Sample Size Determination**

We estimated the incidences of tube dislodgement to be 20 per 1000 ventilator days and the incidence of lip ulcer development in the previous 12 months was 1.1 per 1000 ventilator days. Using the sum of these overall incidences of 21.1 per 1000 ventilator days and a standard deviation of 15 per 1000 ventilator days, we calculated a need for 142 patients in each arm to detect a clinically meaningful change of 5 episodes per 1000 ventilator days with 80% power at a two-sided alpha level of 0.05. We plan to enroll 500 patients which would allow for a 5.6% dropout or loss to follow-up rate. We used PS software to calculate the sample size.

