### **12.3 Baseline Characteristics**

Principal Investigator: [name], ACNP-BC  
Study Title: Adhesive Versus Endotracheal Tube Fastener  
Institution: Vanderbilt University Medical Center

Version Date: 3/21/2018

To assess randomization success, we will summarize in Table 1 the distribution of baseline variables across the study arms. Categorical variables will be reported as frequencies and percentages and continuous variables as either means with SDs or medians with interquartile ranges. Variables reported will include Demographics (age, gender, race, BMI); Indication for intubation; Active illnesses at the time of intubation; Severity of Illness (APACHE II score, blood pressure); Location of intubation (ICU, ED, OSH)

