#### **12.4 Primary Analyses**

The primary endpoint will be the continuous variable of incidences of lip ulcers, tube dislodgement, or ventilator associated pneumonia per 1,000 ventilator days. The differences between the two groups will be compared using the Mann-Whitney U test. All other comparisons will be considered secondary analyses.

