#### **12.5 Secondary Analyses**

*Analysis of Secondary and Tertiary Outcomes.*

We will conduct unadjusted analysis examining the treatment effect of endotracheal tube securement method on each of the pre-specified secondary and tertiary outcomes. Continuous outcomes will be compared with the Mann-Whitney U test and categorical variables with the Chi-square or Fisher Exact testing as appropriate.

*Subgroup Analyses.*

We will conduct unadjusted analysis examining the treatment effect of endotracheal tube securement technique on incidence of lip ulcers, tube dislodgement, and VAP in each of the pre-specified subgroups. Data will be presented as odds ratios and 95% confidence intervals for categorical variables and as mean differences and 95% confidence intervals for continuous variables.

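### No analysis adjusts for baseline factors; a short pre-specified covariate list for the primary estimate would be a cheap gain in precision, though the unadjusted comparison is valid

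*Combined protocol and SAP*

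**What the plan says.** The default in section 12.2 (Analysis principles) is "All analyses will be unadjusted unless otherwise specified". No later section departs from it:

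- **Primary (12.4):** "The differences between the two groups will be compared using the Mann-Whitney U test". That test takes no covariates.
- **Secondary and tertiary (12.5):** "We will conduct unadjusted analysis examining the treatment effect of endotracheal tube securement method". The subgroup paragraph is unadjusted too.
- **Presentation (12.6):** between-group comparisons are limited to Mann-Whitney, chi-square and Fisher tests.

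Randomisation (6.5) uses permuted blocks of size 2, 4 and 6 and names no stratification factor.

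The baseline data are described in three places that do not fully match:

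- Section 8.0 lists age, among others, and "indication for intubation, whether it is a reintubation, whether the face was soiled during the intubation".
- Section 12.3 plans a baseline table that adds APACHE II, blood pressure and "Location of intubation (ICU, ED, OSH"), none of which is in the section 8.0 baseline list. Reintubation is in section 8.0 but not in that table.
- Sections 5.1, 6.2 and 6.3 make intubation before ICU arrival, and its timing, part of eligibility, so that status must be known for every patient.

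The primary endpoint also differs between sections. The Study Summary (1.0) has "Composite of any of: presence of lip ulcer, endotracheal tube dislodgement, or facial skin tears", a yes/no outcome. Section 12.4 has "The primary endpoint will be the continuous variable of incidences of lip ulcers, tube dislodgement, or ventilator associated pneumonia per 1,000 ventilator days".

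**The concern.** The trial pools patients randomised when intubation is decided with patients already intubated for up to 12 hours. The second group had a tube in place before assignment. Reintubated patients and older patients may also differ in tube movement, skin fragility or time at risk. Neither the design (no stratification) nor the analysis (no covariates) uses this information.

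Pre-specified adjustment for a few pre-randomisation factors keeps the type I error. It narrows the interval to the extent that the factors predict the outcome, and it removes their chance imbalance from the estimate. A model would also give the primary comparison an effect estimate with an interval, whereas section 12.4 names only a test. What is at stake is some precision, and a covariate list fixed before outcomes are seen instead of one chosen afterwards.

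**Working it through.** **1. The plan's own figure.** Section 12.1 gives a difference of 5 and an SD of 15 per 1,000 ventilator days, 80% power, "at a two-sided alpha level of 0.05", and 142 per arm.

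n per arm = 2 × [15 × (1.960 + 0.842) / 5]² = 141.3, rounded up to 142. The figure reproduces; power at 142 per arm is 80.2%.

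**2. Effect of adjustment on that calculation.** In a linear model, covariates that explain a share R² of outcome variance reduce the SD to 15 × √(1 − R²). The documents give no R², so the range below is an assumption. The last column is 500 × [1/(1 − R²) − 1].

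| R² | n per arm, 80% power | Power, 142 per arm | Power, 250 per arm | Interval narrower by | Extra patients on 500 |
|---|---|---|---|---|---|
| 0 | 142 | 80.2% | 96.1% | 0% | 0 |
| 0.02 | 139 | 81.0% | 96.4% | 1.0% | 10 |
| 0.05 | 135 | 82.2% | 96.9% | 2.5% | 26 |
| 0.10 | 128 | 84.2% | 97.5% | 5.1% | 56 |

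**3. Cross-check for a binary composite.** Simulation with 250 per arm, one continuous covariate, 1,000 runs per scenario and assumed risks. It compared unadjusted and covariate-adjusted risk differences from linear regression with robust standard errors.

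| Assumed risks | Log-odds ratio per SD of covariate | Variance explained | Power unadjusted | Power adjusted |
|---|---|---|---|---|
| 15% v 7% | 0 | 0.2% | 80.0% | 80.1% |
| 15% v 7% | 0.5 | 2.4% | 81.5% | 83.0% |
| 15% v 7% | 1.0 | 8.0% | 84.9% | 87.7% |
| 20% v 11% | 0 | 0.2% | 82.8% | 82.0% |
| 20% v 11% | 0.5 | 3.3% | 81.2% | 82.0% |
| 20% v 11% | 1.0 | 10.1% | 82.3% | 85.6% |

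Each power value has a simulation standard error of about √(0.8 × 0.2/1,000) = 1.3 points. A useless covariate makes little difference either way. A useful one adds roughly 1 to 3 points.

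**4. Chance imbalance.** For a factor present in 30% of patients (assumption), the between-arm difference has standard error √(2 × 0.3 × 0.7/250) = 4.1 points, a 95% range of about ±8 points. If that factor raised risk by 10 points (assumption), a 4.1-point imbalance would move the risk difference by 0.041 × 10 = 0.4 points.

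**5. How many covariates the data can carry.** At 21.1 events per 1,000 ventilator days (dislodgement plus lip ulcer, section 12.1), 500 patients with an assumed mean of 3 to 10 ventilator days give 500 × 3 × 0.0211 = 32 to 500 × 10 × 0.0211 = 106 events. Treatment plus three single-parameter covariates is four parameters, or about 8 to 26 events per parameter. Skin tears or pneumonia would add events; the documents give no rate for either.

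**The case against.** The strongest reply is that this is a preference. An unadjusted intention-to-treat comparison in an unstratified 1:1 trial controls the type I error. The choice is pre-specified and consistent across sections 12.2 to 12.6, and no stratification factor is left out. All of that stands. A reader might infer from the missing covariates that the primary analysis is biased or invalid; the documents do not support that. The unadjusted interval already allows for chance imbalance, and step 4 shows that its typical effect on the estimate is small.

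A reader might also infer that the recorded factors are known to be related to the outcomes. No section says so; it is clinical plausibility only, and R² could be near zero. Nor is the baseline table shown to be their only use, because section 12.5 refers to pre-specified subgroups that are never listed.

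Nor is the change free. It replaces the primary test and effect measure, and an adjusted odds ratio estimates a different quantity from an unadjusted one. A standardised risk difference avoids the second problem, and a short list answers most of the sparse-event objection.

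Finally, unadjusted power at 250 per arm is already 96.1%, which leaves little to gain. That figure is weak support. It needs the SD of 15, which section 12.1 does not justify for per-patient rates: under a Poisson rate of 21.1 per 1,000 days, a patient observed for 5 days has a rate SD of √(0.0211/5) = 0.065, or 65 per 1,000. It also needs the full 500, which does not follow from 142 per arm and 5.6% loss (284/0.944 = 301). Adjustment would not repair either problem, but 96.1% is no reason to dismiss precision.

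**Conclusion.** The point holds as an optional efficiency improvement. Every analysis is unadjusted, and a few usable baseline factors enter no specified model. The gain is zero if they do not predict the outcome and about 10, 26 or 56 patient-equivalents on 500 if they explain 2%, 5% or 10% of variance. That rests on assumed R² values and a linear-model formula, which only approximates a logistic or count model. On the plan's own SD, R² of 10% adds 4.0 points of power at 142 per arm and 1.4 points at 250 per arm. No error in the planned comparison is shown, and the improvement ranks below settling the primary endpoint, without which no adjusted model can be chosen.

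**What to change.** 1. First reconcile the primary endpoint between the Study Summary (1.0) and section 12.4.
2. In section 12.4, pre-specify the primary estimate as a model of that endpoint on treatment plus age, reintubation, and intubated before ICU arrival or not. Add APACHE II only if it is scored from pre-randomisation data; the documents do not state its timing.
3. For the binary composite, use logistic regression with a standardised risk difference and a robust interval. If a rate is kept, use a count model that allows for overdispersion, with log ventilator-days as offset.
4. Leave out face soiling for patients randomised before intubation. Under section 6.5 the envelope is opened once intubation is judged necessary, so soiling during the procedure is recorded after assignment is known.
5. Report the unadjusted result as a sensitivity analysis, and amend the default in section 12.2 to match.
6. State a simple rule for missing covariates, and make the baseline lists in sections 8.0 and 12.3 agree.

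**Cost:** SAP wording and one model. Age and reintubation are already collected, and pre-ICU intubation is needed for eligibility. The downsides are that the primary test and effect measure move away from Mann-Whitney, missing covariates need handling, and the expected event count keeps the list short.

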#### **Trial profile:**

- We will present a Consolidated Standards of Reporting Trials diagram as Figure 1 to detail the movement of patients through the study. This diagram will include total number of patients meeting inclusion criteria, number excluded and reason for exclusion, number enrolled and randomized in the study, number followed, and number analyzed.

### **12.3 Baseline Characteristics**

Principal Investigator: [name], ACNP-BC  
Study Title: Adhesive Versus Endotracheal Tube Fastener  
Institution: Vanderbilt University Medical Center

Version Date: 3/21/2018

To assess randomization success, we will summarize in Table 1 the distribution of baseline variables across the study arms. Categorical variables will be reported as frequencies and percentages and continuous variables as either means with SDs or medians with interquartile ranges. Variables reported will include Demographics (age, gender, race, BMI); Indication for intubation; Active illnesses at the time of intubation; Severity of Illness (APACHE II score, blood pressure); Location of intubation (ICU, ED, OSH)

#### **12.4 Primary Analyses**

The primary endpoint will be the continuous variable of incidences of lip ulcers, tube dislodgement, or ventilator associated pneumonia per 1,000 ventilator days. The differences between the two groups will be compared using the Mann-Whitney U test. All other comparisons will be considered secondary analyses.

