### **Study Aims:**

#### **Primary:**

- To compare the effect of adhesive tape versus endotracheal tube fasteners on adverse effects (lip ulcers, endotracheal tube dislodgement, or facial skin tears) among critically ill adults undergoing endotracheal intubation

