### **Study Hypotheses:**

#### **Primary:**

- The use of an endotracheal tube fastener will reduce the incidence of any of lip ulcers, endotracheal tube dislodgement, or facial skin tears among critically ill adults undergoing endotracheal intubation

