**Secondary:**

- The use of endotracheal tube fastener will reduce the incidence of endotracheal tube dislodgement, ventilator associated pneumonia, and facial skin tears among critically ill adults undergoing endotracheal intubation
- The use of endotracheal tube fastener will increase the number of ventilator-free days among critically ill adults undergoing endotracheal intubation

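### Sections 1.0 and 12.4 name different primary endpoints, 12.1 is sized on a third set of components, and the follow-up windows disagree

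*Combined protocol and SAP*

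**What the plan says.** Section 12.4 defines the primary endpoint as a rate: "The primary endpoint will be the continuous variable of incidences of lip ulcers, tube dislodgement, or ventilator associated pneumonia per 1,000 ventilator days". The arms are compared by Mann-Whitney U, and "All other comparisons will be considered secondary analyses". The primary aim and hypothesis in Section 1.0 and the subgroup analyses in 12.5 use the same three components.

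The Primary Endpoint entry in Section 1.0 differs: "Composite of any of: presence of lip ulcer, endotracheal tube dislodgement, or facial skin tears", counted "from the time of randomization to the earlier of death or 48 hours after extubation". The secondary list directly below it includes "Ventilator associated pneumonia incidence".

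Section 3.0 sides with that entry. Its primary hypothesis is that the fastener "will reduce the incidence of any of lip ulcers, endotracheal tube dislodgement, or facial skin tears", and VAP appears only in the secondary hypothesis, that the fastener "will reduce the incidence of endotracheal tube dislodgement, ventilator associated pneumonia, and facial skin tears". Section 4.0 lists all four outcomes without ranking them.

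Section 12.1 sizes the trial on dislodgement (20 per 1,000 ventilator days) plus lip ulcer (1.1), with neither VAP nor skin tears. Section 8.0 stops collecting endpoint events at death, discharge, tracheostomy or 48 hours after extubation. Section 14.0 ends patient follow-up at 28 days or discharge.

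**The concern.** A confirmatory trial needs one primary endpoint, and this plan labels two. Followed literally, 12.4 leaves skin tears out of the confirmatory test and puts in VAP, which Section 1.0 calls secondary. The Section 3.0 primary hypothesis is then not tested in full. The composite is not in the secondary list either, so no section names it as an outcome to be compared.

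A reader of the results could not tell which p-value answers the trial's question. The two labels also leave room to pick a version after the data are seen. Finally, the 80% power in 12.1 describes neither endpoint.

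**Working it through.** **Side by side**

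| Place | Lip ulcer | Dislodgement | Skin tears | VAP | Scale |
|---|---|---|---|---|---|
| 1.0 Primary Endpoint | yes | yes | yes | no | any event per patient |
| 3.0 primary aim and hypothesis | yes | yes | yes | no | incidence (hypothesis: any of the three) |
| 1.0 primary aim and hypothesis | yes | yes | no | yes | incidence |
| 12.4 | yes | yes | no | yes | rate per 1,000 ventilator days |
| 12.1 | yes | yes | no | no | rate, compared as means |

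Section 1.0 therefore also conflicts within itself.

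**The plan's own sample size.** Inputs from 12.1: difference 5, SD 15, two-sided alpha 0.05, power 80%. n per arm = 2 × (1.960 + 0.842)² × 15² / 5² = 141.3, so 142, as stated. At 250 per arm (500/2, no dropout), 5 / (15 × √(2/250)) = 3.727 and power = Φ(3.727 − 1.960) = 96%. This is a two-means calculation on a component set that neither endpoint uses.

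**Share of events.** The shared components total 20 + 1.1 = 21.1 per 1,000 days, and dislodgement is 20/21.1 = 95% of that. The documents give no VAP or skin-tear rate, so the rate r of the unshared component is assumed. The share of a version's events that the other does not count is r / (21.1 + r):
- r = 1: 1/22.1 = 4.5%
- r = 3: 3/24.1 = 12.4%
- r = 12: 12/33.1 = 36.3%

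**Share of patients.** Assume independent Poisson events over a fixed d ventilator days (3, 7 or 14, also assumed). Let S = 0.0211d, and let T and V be the expected skin-tear and VAP counts per patient.
- P(counted by one version only) = e^−S × [(1 − e^−T)e^−V + (1 − e^−V)e^−T]
- P(any event) = 1 − e^−(S+T+V)
- Example, 7 days and 3 per 1,000 each: e^−0.1477 × 2 × (1 − e^−0.021) × e^−0.021 = 0.0351; 1 − e^−0.1897 = 0.1728; ratio 20%.

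| Assumed rates per 1,000 days | Patients with any event who count under one version only |
|---|---|
| 1 and 1 | 7% to 8% |
| 3 and 3 | 19% to 21% |
| 12 and 3 | 34% to 40% |
| 12 and 12 | 42% to 51% |

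**False positives if the version is chosen after results.** Null simulation: 4,000 trials in each of 15 settings, 250 per arm, ventilator days 1 plus an exponential with mean total 3, 7 or 14, shared rate 21.1. Chi-square on the composite alone and tie-corrected Mann-Whitney on the rate alone each rejected in 4% to 6% of trials. At least one rejected in 6.0% to 6.7% at rates of 1 and 1, and in 6.8% to 9.6% at rates of 3 to 12. A rerun of the same settings peaked just under 9%, so the upper end carries simulation error.

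**Windows.** Section 1.0 counts events up to death or 48 hours after extubation. Section 8.0 also stops at discharge and tracheostomy, so events that Section 1.0 counts could go uncollected. Section 14.0 would end follow-up at day 28 even for a patient still intubated.

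**The case against.** The strongest reply is that the practical gap is small. Dislodgement dominates both versions, the larger overlap figures rest on assumed rates and stays, and at 1 per 1,000 the versions nearly coincide. The inflated error rate requires a choice after results, which no section proposes. All of this stands, and the size should be read accordingly. It does not settle which endpoint is primary.

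Section 12.6 prescribes chi-square or Fisher's exact for all categorical comparisons, so a default test exists for the composite, and its three components are each listed as secondary. That is right, but no section names the composite itself for comparison.

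Section 12.1 shares the rate scale of 12.4 and two of its three components, and sizing a rank test by a two-means formula is a common approximation. This narrows the mismatch with 12.4 to the missing VAP and the approximation; it does not remove it.

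Section 14.0 describes general follow-up, not an endpoint window. That makes it the weaker part of the window point. The conflict between Sections 1.0 and 8.0 is direct, although the documents do not show how many events it affects.

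**Conclusion.** The concern holds. The current text names two primary endpoints with different components, scales and tests, and nothing in it decides between them. The 12.4 analysis would not test the Section 1.0 endpoint, or the Section 3.0 primary hypothesis, in full. This is a contradiction to be corrected, not a missing detail.

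The numerical size is uncertain. Under assumed VAP and skin-tear rates of 3 to 12 per 1,000 days, 12% to 36% of each version's events, and 19% to 51% of patients with any event, fall under one version only; at 1 per 1,000 the figures are about 5% and 7% to 8%. Type I error stays near 5% if 12.4 is followed, and is about 6% to 10% only if the version is picked afterwards.

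**What to change.** Before any comparison by arm, the sponsor should state one primary endpoint with its components, scale, test and a single follow-up window, and list the other version as secondary. Either version is acceptable.

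- If the Section 1.0 composite is chosen: compare it by chi-square, with a risk difference and 95% confidence interval.
- If the 12.4 rate is kept: count ventilator days over the same window as the events.
- Align Section 1.0 (title, background, aim, hypothesis, endpoints), Section 3.0 (rationale, aims, hypotheses), Section 8.0, Sections 12.1, 12.4 and 12.5, and Section 14.0.
- Restate the power in 12.1 for the chosen endpoint and test, with its own components and a per-patient SD or proportion.

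**Cost.** With the Section 8.0 window, ended at day 28 as in Section 14.0, this is a change of wording: all four components are already collected. The Section 1.0 window as written would need data after discharge or tracheostomy that are not now planned. The restated power needs inputs that the documents do not give and may fall well below 80%, mainly because an SD of 15 looks small for per-patient rates. That is a separate problem, which settling the endpoint will not cure. No extra enrolment is proposed.

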Ventilator-free days will be collected from the time of randomization through study day 28. In order to get credit for a ventilator-free day, a patient must be both alive and free of mechanical ventilation. Patients who are extubated and reintubated will only be credited with being free of mechanical ventilation for days after the last extubation. Patients who die before study day 28, regardless of whether or not they ever achieved unassisted breathing, will be assigned zero ventilator-free days. Patients who are still on the ventilator at study day 28 will also receive zero ventilator-free days. Patients who are discharged from the hospital prior to study day 28 free of mechanical ventilation will be assumed to remain free of mechanical ventilation through study day 28. Patients who are discharged from the hospital prior to day 28 on mechanical ventilation will try to be followed at the discharge location for date of extubation – however, if the date is not able to be obtained, they will be assumed to have zero ventilator free days in the analysis.

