#### **12.6 Presentation of Statistics**

Continuous variables will be described as mean and standard deviation or median and 25th percentile – 75th percentile or bootstrapped 95% confidence intervals as appropriate. Categorical variables will be given as percentage and number. All between-group comparisons with continuous variables will be performed using Mann-Whitney U tests and Chi-square or Fisher's exact test for categorical variables

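### The primary per-ventilator-day rate is tested by unadjusted Mann-Whitney, which does not compare that rate and rejects too often when ventilation time differs by arm

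*Combined protocol and SAP*

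**What the plan says.** - Section 12.4 (Primary Analyses) defines the variable: "The primary endpoint will be the continuous variable of incidences of lip ulcers, tube dislodgement, or ventilator associated pneumonia per 1,000 ventilator days". It then names the test: "The differences between the two groups will be compared using the Mann-Whitney U test".
- Section 12.2 leaves analyses unadjusted by default, and Section 12.6 repeats Mann-Whitney for every continuous comparison. The only interval mentioned for continuous variables there is descriptive: "bootstrapped 95% confidence intervals as appropriate". Section 12.5 offers mean differences with intervals, but only for subgroups. Nowhere is there an exposure offset, person-time weighting or a rate ratio.
- Section 12.1 sizes the trial on the same kind of quantity: "Using the sum of these overall incidences of 21.1 per 1000 ventilator days", with a difference of 5 per 1,000 to detect. The 21.1 is 20 for dislodgement plus 1.1 for lip ulcer; ventilator associated pneumonia (VAP) is not included.
- Section 3.0 (secondary hypotheses) expects a duration effect: "The use of endotracheal tube fastener will increase the number of ventilator-free days".
- Section 8.0 collects events "anytime between randomization and the earlier of death, hospital discharge, tracheostomy placement, or 48 hours after extubation". No matching window is given for the ventilator-day denominator. Section 8.0 lists days on the ventilator and Section 14.0 limits follow-up to 28 days or discharge, but neither defines the denominator of the rate.
- Section 1.0 gives a different primary endpoint: "Composite of any of: presence of lip ulcer, endotracheal tube dislodgement, or facial skin tears".

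**The concern.** A rate per 1,000 ventilator days is meant to remove the effect of how long patients are ventilated. A rank test on per-patient rates does not do that when events are rare. A patient with no event scores zero whether ventilated for 2 days or 20, so duration affects the rank only among the few patients with an event. What remains is mostly a comparison of the proportion with any event, and that proportion rises with time at risk even when the daily rate is the same.

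If the fastener arm is ventilated for less time, as the plan hopes, the primary test could report a lower incidence per ventilator day where none exists. The reverse can also happen: a truly lower daily rate can be hidden if that arm is ventilated longer. The plan also specifies no rate ratio with an interval, so a reader could not see the discrepancy.

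**Working it through.** **1. The plan's own figure.** Two-sided alpha 0.05, power 80%, difference 5, SD 15: n = 2 × (1.960 + 0.842)² × 15² / 5² = 2 × 7.85 × 9 ≈ 141.3, so 142 per arm, as in Section 12.1. This is a calculation for a difference in mean rates, which Mann-Whitney does not test.

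**2. Inputs for the check.** From the plan: rate 21.1 per 1,000 ventilator days in both arms; 500 enrolled with 5.6% loss, so 500 × 0.944 = 472, or 236 per arm; two-sided 0.05. Assumed, because the documents give no ventilation times: lognormal stays (log-SD 0.8), mean 5, 7 or 10 days, capped at 28; constant hazard; the patient as unit (Section 12.4 does not state one).

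**3. How many tie at zero.** If every stay equalled the mean, the zero share would be exp(−0.0211 × days): 0.90, 0.86 and 0.81 for 5, 7 and 10 days. With lognormal stays the simulated shares are 90.5, 87.1 and 82.8%.

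**4. Rejection rate when the true per-day rates are identical.** Events ~ Poisson(0.0211 × days); patient rate = 1,000 × events / days; 4,000 simulated trials per setting (Monte Carlo SE at 5%: √(0.05 × 0.95 / 4,000) = 0.34 points). Entries are % for mean stays of 5 / 7 / 10 days.

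| Stay in one arm | Mann-Whitney | Rate ratio, log offset, robust errors |
|---|---|---|
| Equal | 5.2 / 5.2 / 4.6 | 5.3 / 4.4 / 4.2 |
| 10% shorter | 6.5 / 5.7 / 6.5 | 5.6 / 5.0 / 4.9 |
| 20% shorter | 9.8 / 10.4 / 11.6 | 4.5 / 4.5 / 5.0 |
| 33% shorter | 17.4 / 21.9 / 24.7 | 4.3 / 4.9 / 4.3 |

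At 20% and 33% shorter, about 95% or more of the rejections favour the shorter-stay arm; at 10% shorter, roughly 76 to 88% do. Chi-square on any event behaves like Mann-Whitney (10.6 / 12.1 / 13.4 at 20% shorter; 19.5 / 25.9 / 30.5 at 33% shorter), which confirms what the rank test is mainly measuring.

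**5. Sensitivity.**
- VAP adding an assumed 5 to 10 per 1,000: Mann-Whitney 9.9 to 13.1% (20% shorter) and 21.2 to 30.7% (33% shorter); offset model 4.2 to 5.9%.
- 142 per arm, mean 7 days: Mann-Whitney 5.0, 8.3 and 16.1% at 10, 20 and 33% shorter.
- 250 per arm, shorter-arm mean 4 to 10 days, other arm 1.25 or 1.5 times as long: Mann-Whitney 9.6 to 13.8% and 24 to 35%.
- Events clustered within patients (gamma frailty, variance 2), 33% shorter: Mann-Whitney 16.9 / 17.8 / 18.5; offset model with robust errors 5.4 / 5.6 / 5.6; plain Poisson 7.6 / 9.5 / 11.3. Robust errors are therefore needed.

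**6. A case that can be checked by hand (deliberately extreme).** 250 per arm, every patient ventilated 10 days in one arm and 5 in the other; 50 and 25 patients have one event each. Rates: 50 / 2,500 = 25 / 1,250 = 20 per 1,000, identical. Mann-Whitney: U = 50 × 225 + ½ × 200 × 225 = 33,750 against an expected 31,250; tie-corrected SD ≈ 1,002; z ≈ 2.49, p = 0.013. Rate ratio 1.00; robust SE of its log = √(40/50² + 22.5/25²) = √0.052 = 0.228, so 95% CI 0.64 to 1.56.

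**7. The converse.** True rates 21.1 v 16.1, the lower-rate arm ventilated 1.31 times as long (mean 7 days, 250 per arm): Mann-Whitney rejects 5.0%, the person-time test 20 to 22%.

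**The case against.** The strongest reply is that the fault is conditional. With equal ventilation time, and so also if the device does nothing at all, Mann-Whitney holds its 5%. The documents give no ventilation time and no expected difference, and at 10% the excess is small. The ventilator-free-days hypothesis is only indirect support: patients who die before day 28 "will be assigned zero ventilator-free days", so that outcome can differ without ventilation time differing. This stands: a difference by arm is plausible, but its size is unknown.

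Second, Section 1.0 and the aims in Section 3.0 point to a composite with skin tears. If that governs, this test no longer concerns the primary endpoint. That also stands, but Section 12.4 is the only place that specifies a primary analysis.

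Third, the unit is not stated, and an SD of 15 does not fit patient-level rates (simulated SD about 63 to 95 per 1,000). However, Section 12.1 counts patients per arm, the patient is randomised, and a rank test needs one value per unit.

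Fourth, the offset model is not free of duration effects. With an assumed threefold hazard in the first 2 days and stays 33% shorter, it rejects 7.1 to 8.5% (Mann-Whitney 10.9 to 14.5%). With a tenfold early hazard it rejects 13 to 19% and Mann-Whitney 6 to 7%; with no risk in the first 2 to 3 days, 8 to 14% against 40 to 51%. In those settings, though, the average rates per day really differ between arms, so these rejections are not errors for the quantity the plan names. They show a limit of the per-day rate as a summary, which should be acknowledged.

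**Conclusion.** The concern holds. The named test does not target the rate that Section 12.4 defines and Section 12.1 plans on. Under the stated assumptions, its false-positive rate for equal per-day rates is about 5% with equal stays, 6 to 7% at 10% shorter, 10 to 12% at 20% shorter and 17 to 25% at 33% shorter. These are conditional illustrations, not a forecast for this trial: they rest on assumed stay lengths, a constant hazard and the patient as unit. The mismatch between test and endpoint does not depend on those assumptions; only its size does. It should be corrected before analysis, with moderate confidence about how much it would matter in practice.

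**What to change.** 1. Reconcile Sections 1.0 and 12.4 and state which primary endpoint governs.
2. If the rate is kept, as primary or secondary, replace Mann-Whitney with Poisson or negative binomial regression of each patient's event count, with log(days at risk) as offset and robust errors. Report the rate ratio and 95% CI.
3. Count events and days at risk over one stated window. At present events stop at tracheostomy and run to 48 hours after extubation, while the denominator has no defined window. If the window includes time off the ventilator, the denominator is no longer ventilator days and should be renamed.
4. Report by arm any patients with no days at risk, since they contribute nothing to the model.
5. If the yes/no composite is chosen, chi-square with a risk difference and CI is valid for cumulative risk, but it also depends on ventilation time and must not be described as a test of the daily rate.

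The cost is SAP wording and a few lines of code on the same data. The trade-off is a model in place of a rank test, and reliance on the average daily rate as a meaningful summary. It costs no power here: for 21.1 v 16.1 with equal stays (236 per arm, means 5 / 7 / 10 days), power is 13.2 / 18.0 / 22.4% for the rate ratio against 12.6 / 15.7 / 18.8% for Mann-Whitney. Both are low, which is a separate matter.
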